Examples: individuals with Traumatic Brain Injury (TBI) or dementia; individuals who are unconscious, or who are significantly intoxicated.

No

Yes

→ If no, go to [question 8.9](#).

→ If yes, answer the following questions.

a. Rationale. Provide the rationale for including this population.

b. Capacity for consent / decision making capacity. Describe the process that will be used to determine whether a cognitively impaired individual is capable of consent decision making with respect to the research protocol and setting.

b.1. If there will be repeated interactions with the impaired subjects over a time period when cognitive capacity could increase or diminish, also describe how (if at all) decision-making capacity will be re-assessed and (if appropriate) consent obtained during that time.

c. Permission (surrogate consent). If the research will include adults who cannot consent for themselves, describe the process for obtaining permission (“surrogate consent”) from a legally authorized representative (LAR).

For research conducted in Washington State, see the [GUIDANCE: Legally Authorized Representative](#) to learn which individuals meet the state definition of “legally authorized representative”.

d. Assent. Describe whether assent will be required of all, some, or none of the subjects. If some, indicate which subjects will be required to assent and which will not (and why not). Describe any process that will be used to obtain and document assent from the subjects.

e. Dissent or resistance. Describe how a subject’s objection or resistance to participation (including non-verbal) during the research will be identified, and what will occur in response.

8.9 Research use of human fetal tissue obtained from elective abortion. Federal and UW Policy specify some requirements for the consent process. If you are conducting this type of research, check the boxes to confirm these requirements will be followed.

- Informed consent for the donation of fetal tissue for research use will be obtained by someone other than the person who obtained the informed consent for abortion.
- Informed consent for the donation of fetal tissue for research use will be obtained after the informed consent for abortion.
- Participation in the research will not affect the method of abortion.
- No enticements, benefits, or financial incentives will be used at any level of the process to incentivize abortion or the donation of human fetal tissue.
- The informed consent form for the donation of fetal tissue for use in research will be signed by both the

woman and the person who obtains the informed consent.

8.10 Consent-related materials. Upload to **Zipline** all consent scripts/talking points, consent forms, debriefing statements, Information Statements, Short Form consent forms, parental permission forms, and any other consent-related materials that will be used. Materials that will be used by a specific site should be uploaded to that site's **Local Site Documents** page.

- *Translations must be submitted and approved before they can be used. However, we strongly encourage you to wait to provide them until the IRB has approved the English versions.*
- *Combination forms: It may be appropriate to combine parental permission with consent, if parents are subjects as well as providing permission for the participation of their children. Similarly, a consent form may be appropriately considered an assent form for older children.*
- *For materials that cannot be uploaded: upload screenshots or written descriptions that are sufficient to enable the IRB to understand the types of data that will be collected and the nature of the experience for the participant. URLs (website addresses) may also be provided, or written descriptions of websites. Examples of materials that usually cannot be uploaded: mobile apps; computer-administered test; licensed and restricted standardized tests.*

9 PRIVACY AND CONFIDENTIALITY

9.1 Privacy protections. Describe the steps that will be taken, if any, to address possible privacy concerns of subjects and potential subjects.

Privacy refers to the sense of being in control of access that others have to ourselves. This can be an issue with respect to recruiting, consenting, sensitivity of the data being collected, and the method of data collection.

Examples:

- *Many subjects will feel a violation of privacy if they receive a letter asking them to participate in a study because they have _____ medical condition, when their name, contact information, and medical condition were drawn from medical records without their consent. Example: the IRB expects that "cold call" recruitment letters will inform the subject about how their information was obtained.*
- *Recruiting subjects immediately prior to a sensitive or invasive procedure (e.g., in an outpatient surgery waiting room) will feel like an invasion of privacy to some individuals.*
- *Asking subjects about sensitive topics (e.g. details about sexual behavior) may feel like an invasion of privacy to some individuals.*

This is a quality improvement research study that intends to improve the standard processes of care for OMC cancer patients regarding genetic counseling and genetic testing. All collection and review of patients' information and medical records will be part of their clinical care and screening. The patients' information will not be used for any type of enrollment or recruitment. The OMC providers (study's subjects) will grant permissions for the release of their patients' medical records to the SCCA study team by reviewing a consent information sheet and sending emailed consent to the study's research coordinator.

9.2 Identification of individuals in publications and presentations. Will potentially identifiable information about subjects be used in publications and presentations, or is it possible that individual identities could be inferred from what is planned to be published or presented?

No

Yes → If yes, will subject consent be obtained for this use?

Yes

→ If no, describe the steps that will be taken to protect subjects (or small groups of subjects) from being identifiable.

9.3 State mandatory reporting. Each state has reporting laws that require some types of individuals to report some kinds of abuse, and medical conditions that are under public health surveillance. These include:

- Child abuse
- Abuse, abandonment, neglect, or financial exploitation of a vulnerable adult
- Sexual assault
- Serious physical assault
- Medical conditions subject to mandatory reporting (notification) for public health surveillance

Are you or a member of the research team likely to learn of any of the above events or circumstances while conducting the research **AND** feel obligated to report it to state authorities?

No

Yes → If yes, the UW IRB expects subjects to be informed of this possibility in the consent form or during the consent process, unless you provide a rationale for not doing so:

9.4 Retention of identifiers and data. Check the box below to indicate assurance that any identifiers (or links between identifiers and data/specimens) and data that are part of the research records will not be destroyed until after the end of the applicable records retention requirements (e.g. Washington State; funding agency or sponsor; Food and Drug Administration). If it is important to say something about destruction of identifiers (or links to identifiers) in the consent form, state something like “the link between your identifier and the research data will be destroyed after the records retention period required by state and/or federal law.”

This question can be left blank for conversion applications (existing paper applications that are being “converted” into a Zipline application.)

See the “Research Data” sections of the following website for UW Records management for the Washington State research records retention schedules that apply in general to the UW (not involving UW Medicine data):

<http://f2.washington.edu/fm/recmgt/gs/research?title=R>

See the “Research Records and Data” information in Section 8 of this document for the retention schedules for UW Medicine Records: <https://www.uwmedicine.org/recordsmanagementuwm-records-retention-schedule.pdf>

Confirm

9.5 Certificates of Confidentiality. Will a federal Certificate of Confidentiality be obtained for the research data?

NOTE: Answer “No” if the study is funded by NIH or the CDC, because all NIH-funded and CDC-funded studies automatically have a Certificate.

No

Yes

9.6 Data and specimen security protections. Identify the data classifications and the security protections that will be provided for all sites where data will be collected, transmitted, or stored, referring to the [ZIPLINE GUIDANCE: Data and Security Protections](#) for the minimum requirements for each data classification level. ***It is not possible to answer this question without reading this document. Data security protections should not conflict with records retention requirements.***

a. Which level of protections will be applied to the data and specimens? If more than one level will be used, describe which level will apply to which data and which specimens and at which sites.

b. Use this space to provide additional information, details, or to describe protections that do not fit into one of the levels. If there are any protections within the level listed in 9.6.a which will *not* be followed, list those here, including identifying the sites where this exception will apply.

All level 4 data collected by OMC will be part of their standard processes of care. The only individual outside of OMC to have access to the identified data will be the study's research coordinator at SCCA. The research coordinator will follow all user, device, server, and data transmission guidelines. Any information provided to the SCCA subject matter experts will be deidentified.

10 RISK / BENEFIT ASSESSMENT

10.1 **Anticipated risks.** Describe the reasonably foreseeable risks of harm, discomforts, and hazards to the subjects and others of the research procedures. For each harm, discomfort, or hazard:

- Describe the magnitude, probability, duration, and/or reversibility of the harm, discomfort, or hazard, AND
- Describe how the risks will be reduced or managed. Do not describe data security protections here, these are already described in Question 9.6.
- Consider possible physical, psychological, social, legal, and economic harms, including possible negative effects on financial standing, employability, insurability, educational advancement or reputation. For example, a breach of confidentiality might have these effects.
- Examples of "others": embryo, fetus, or nursing child; family members; a specific group.
- Do not include the risks of non-research procedures that are already being performed.
- If the study design specifies that subjects will be assigned to a specific condition or intervention, then the condition or intervention is a research procedure - even if it is a standard of care.
- Examples of mitigation strategies: inclusion/exclusion criteria; applying appropriate data security measures to prevent unauthorized access to individually identifiable data; coding data; taking blood samples to monitor something that indicates drug toxicity.
- As with all questions on this application, you may refer to uploaded documents.

Participation in this study involves a time commitment from the OMC provider subjects in which they are required to designate time from their schedule to participate in bi-monthly virtual conferences. If a participant decides to implement the coaching from SCCA in their clinical care, time will be required to discuss genetic counseling and testing with their eligible patients, ordering genetic testing, and allocating extra time at patient follow-up visits to review genetic results. This time commitment may cause stress in the OMC provider subjects because it will likely require them to change how they manage their schedules.

This study requires OMC provider subjects to grant permissions to SCCA to collect their patients' medical records, which may pose security concerns and a breach of confidentiality for their patients.

10.2 **Reproductive risks.** Are there any risks of the study procedures to men and women (who are subjects, or partner of subjects) related to pregnancy, fertility, lactation or effects on a fetus or neonate?

Examples: direct teratogenic effects; possible germline effects; effects on fertility; effects on a woman's ability to continue a pregnancy; effects on future pregnancies.

	No
	Yes

→ If no go to [question 10.3](#)

→ If yes, answer the following questions:

a. Risks. Describe the magnitude, probability, duration and/or reversibility of the risks.

b. Steps to minimize risk. Describe the specific steps that will be taken to minimize the magnitude, probability, or duration of these risks.

Examples: inform the subjects about the risks and how to minimize them; require a pregnancy test before and during the study; require subjects to use contraception; advise subjects about banking of sperm and ova.

If the use of contraception will be required: describe the allowable methods and the time period when contraception must be used.

c. Pregnancy. Describe what will be done if a subject (or a subject's partner) becomes pregnant

For example; will subjects be required to immediately notify study staff, so that the study procedures can be discontinue or modified, or for a discussion of risks, and/or referrals or counseling?

10.3 MRI risk management. Answer this question only if the subjects will receive MRI scans. A rare but serious adverse reaction called nephrogenic systemic fibrosis (NSF) has been observed in individuals with kidney disease who received gadolinium-based contrast agents (GBCAs) for the scans. Also, a few healthy individuals have a severe allergic reaction to GBCAs.

a. Describe how the renal function of subjects will be assessed prior to MRI scans and how that information will be used to exclude subjects at risk for NSF.

N/A, subjects will not receive MRI scans

b. Describe the protocol for handling a severe allergic reaction to the GBCA or any other medical event/emergency during the MRI scan, including who will be responsible for which actions.

N/A, subjects will not receive MRI scans

10.4 Unforeseeable risks. Are there any research procedures that may have risks that are currently unforeseeable?

Example: using a drug that hasn't been used before in this subject population.

No

Yes

→ If yes, identify the procedures.

10.5 Subjects who will be under regional or general anesthesiology. Will any research procedures occur while patients are under general or regional anesthesia, or during the 3 hours preceding general or regional anesthesia (supplied for non-research reasons)?

No

Yes

→ If yes, check all the boxes that apply.

Administration of any drug for research purposes

Inserting an intra-venous (central or peripheral) or intra-arterial line for research purposes

Obtaining samples of blood, urine, bone marrow or cerebrospinal fluid for research purposes

Obtaining a research sample from tissue or organs that would not otherwise be removed during surgery

Administration of a radio-isotope for research purposes**

Implantation of an experimental device

Other manipulations or procedures performed solely for research purposes (e.g., experimental liver dialysis, experimental brain stimulation)

If any of the boxes are checked:

Provide the name and institutional affiliation of a physician anesthesiologist who is a member of the research team or who will serve as a safety consultant about the interactions between the research procedures and the general or regional anesthesia of the subject-patients. If the procedures will be performed at a UW Medicine facility or affiliate, the anesthesiologist must be a UW faculty member, and the Vice Chair of Clinical Research in the UW Department of Anesthesiology and Pain Medicine must be consulted in advance for feasibility, safety and billing.

*** If the box about radio-isotopes is checked: the study team is responsible for informing in advance all appropriate clinical personnel (e.g., nurses, technicians, anesthesiologists, surgeons) about the administration and use of the radio-isotope, to ensure that any personal safety issues (e.g., pregnancy) can be appropriately addressed. This is a condition of IRB approval.*

10.6 Data and Safety Monitoring. A Data and Safety Monitoring Plan (DSMP) is required for clinical trials (as defined by NIH). If required for this research, or if there is a DSMP for the research regardless of whether it is required, upload the DSMP to **Zipline**. If it is embedded in another document being uploading (for example, a Study Protocol) use the text box below to name the document that has the DSMP. Alternatively, provide a description of the DSMP in the text box below.

The OMC provider subjects will be given detailed instructions (both written and verbal) on how to collect relevant patient data and send electronically to the study's research coordinator (via secure email). Once received by the study's research coordinator, the data will be stored in a secured J-Drive folder within the SCCA network. The research coordinator will randomly assign all identified patient data to a unique participant ID before distributing to SCCA subject matter experts (cancer geneticist and/or genetic counselor) for review. For the bi-monthly conference meetings in which the SCCA subject matter experts review patients' medical records, the study's research coordinator will order the patients for discussion (OMC providers will receive the meeting agendas that lists the patient discussion order which will include patient PHI. SCCA subject matter experts will also receive meeting agendas that lists the same patient discussion order but will only have access to the unique participant ID and no PHI).

10.7 Un-blinding. If this is a double-blinded or single-blinded study in which the participant and/or relevant study team members do not know the group to which the participant is assigned: describe the circumstances under which un-blinding would be necessary, and to whom the un-blinded information would be provided.

N/A. This is not a double-blinded or single-blinded study.

10.8 Withdrawal of participants. If applicable, describe the anticipated circumstances under which participants will be withdrawn from the research without their consent. Also, describe any procedures for orderly withdrawal of a participant, regardless of the reason, including whether it will involve partial withdrawal from procedures and any intervention but continued data collection or long-term follow-up.

10.9 Anticipated direct benefits to participants. If there are any direct research-related benefits that some or all individual participants are likely to experience from taking part in the research, describe them below:

Do not include benefits to society or others, and do not include subject payment (if any). Examples: medical benefits such as laboratory tests (if subjects receive the results); psychological resources made available to participants; training or education that is provided.

This research will improve patient access to genetic testing which would enable us to identify if there are any previously undetected genetic predispositions in a patient's family. As a result, we can offer participation in cancer screening, surveillance, and prevention programs for family members at risk of cancer to decrease their risk to as close to zero as possible. Overall, this study will improve utilization of genetic counseling and testing amongst OMC providers caring for their cancer patients.

10.10 Return of individual research results.

In this section, provide your plans for the return of individual results. An "individual research result" is any information collected, generated or discovered in the course of a research study that is linked to the identity of a research participant. These may be results from screening procedures, results that are actively sought for purposes of the study, results that are discovered unintentionally, or after analysis of the collected data and/or results has been completed.

See the [**GUIDANCE Return of Individual Results**](#) for information about results that should and should not be returned, validity of results, the Clinical Laboratory Improvement Amendment (CLIA), consent requirements and communicating results.

a. Is it anticipated that the research will produce any individual research results that are clinically actionable?

"Clinically actionable" means that there are established therapeutic or preventive interventions or other available actions that have the potential to change the clinical course of the disease/condition, or lead to an improved health outcome.

In general, every effort should be made to offer results that are clinically actionable, valid and pose life-threatening or severe health consequences if not treated or addressed quickly. Other clinically actionable results should be offered if this can be accomplished without compromising the research.

X	No
	Yes

→ If yes, answer the following questions (a.1-a.3).

a.1. Describe the clinically actionable results that are anticipated and explain which results, if any, could be urgent (i.e. because they pose life-threatening or severe health consequences if not treated or addressed quickly).

Examples of urgent results include very high calcium levels, highly elevated liver function test results, positive results for reportable STDs.

a.2. Explain which of these results will be offered to subjects.

a.3. Explain which results will not be offered to subjects and provide the rationale for not offering these results.

Reasons not to offer the results might include:

- *There are serious questions regarding validity or reliability*
- *Returning the results has the potential to cause bias*
- *There are insufficient resources to communicate the results effectively and appropriately*
- *Knowledge of the result could cause psychosocial harm to subjects*

b. What is the plan (if any) for offering subjects any results that are not clinically actionable?

Examples: non-actionable genetic results, clinical tests in the normal range, experimental and/or uncertain results.

	No
	Yes

→ If yes, explain which results will be offered to subjects and provide the rationale for offering these results.

c. Describe the validity and reliability of any results that will be offered to subjects.

The IRB will consider evidence of validity such as studies demonstrating diagnostic, prognostic, or predictive value, use of confirmatory testing, and quality management systems.

The results that will be offered to the OMC provider subjects will be reliable due to the consistent, uniform processes in data collection and recommendation that will be followed throughout the entire course of this study. The results will be valid because the reporting of the numbers of patients meeting criteria, referrals for genetic counseling/testing, completed genetics appointments, and genetic testing results, will be recorded and tracked by the same research coordinator.

d. Describe the process for communicating results to subjects and facilitating understanding of the results. In the description, include who will approach the participant with regard to the offer of results, who will communicate the result (if different), the circumstances, timing, and communication methods that will be used.

Results will be communicated to the OMC provider subjects at the end of phase 1 and phase 2. The SCCA study team and subjects will meet to discuss the number of patients seen who were eligible for genetic testing, number of those patients who were referred for genetic counseling/testing, the number of those patients who complete a genetics appointment, and the number of those patients who chose to undergo genetic testing. The OMC provider subjects will also be sent this data for their review in order to assess their current clinic processes.

e. Describe any plans to share results with family members (e.g. in the event a subject becomes incapacitated or deceased).

N/A

f. Check the box to indicate that any plans for return of individual research results have been described in the consent document. If there are no plans to provide results to participants, this should be stated in the consent form.

See the [GUIDANCE Return of Individual Results](#) for information about consent requirements.

Confirmed

10.11 Commercial products or patents. Is it possible that a commercial product or patent could result from this study?

	No
-------------------------------------	-----------

Yes → If yes, describe whether subjects might receive any remuneration/compensation and, if yes, how the amount will be determined.

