3 NON-UW RESEARCH SETTING

**Complete this section only if UW investigators and people named in the SUPPLEMENT:
Non-UW Individual Investigators will conduct research procedures outside of UW and Harborview**

3.1 Reason for locations. Describe the reason(s) for choosing the locations.

This is especially important when the research will occur in locations or with populations that may be vulnerable to exploitation. One of the three ethical principles the IRB must consider is justice: ensuring that reasonable, non-exploitative, and well-considered procedures are administered fairly, with a fair distribution of costs and potential benefits.

OMC is the ideal site for this research study because of its rural and underserved location, which can pose many obstacles to their patients in accessing genetic evaluations for the treatment of their cancers and for their family members. OMC is an affiliate site of SCCA and this partnership, in which SCCA will provide coaching to OMC providers, will facilitate a more open line of communication between the sites. OMC providers will have the resources to increase access to genetic counseling and testing to its patients as well as refer their patients with more complicated cases to SCCA for genetic consultation services

3.2 Local context. Culturally appropriate procedures and an understanding of local context are an important part of protecting subjects. Describe any site-specific cultural issues, customs, beliefs, or values that may affect the research, how it is conducted, or how consent is obtained or documented.

Examples: It would be culturally inappropriate in some international settings for a woman to be directly contacted by a male researcher; instead, the researcher may need to ask a male family member for permission before the woman can be approached. It may be appropriate to obtain permission from community leaders prior to obtaining consent from individual members of a group. In some distinct cultural groups, signing forms may not be the norm.

This federal site maintains an international list of human research standards and requirements:

<http://www.hhs.gov/ohrp/international/index.html>

N/A

3.3 Location-specific laws. Describe any local laws that may affect the research (especially the research design and consent procedures). The most common examples are laws about:

- **Specimens** – for example, some countries will not allow biospecimens to be taken out of the country.

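### Phase 1 patients whom the experts judge to meet NCCN testing criteria, but who have no referral or test, have no stated route from that judgement to care

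*Protocol*

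**What the plan says.** Section 5.1 describes Phase 1 as existing OMC practice with no intervention. OMC sends identified patient data to the SCCA research coordinator, who replaces identity with a participant ID. SCCA experts then establish how many patients met NCCN testing criteria, how many were referred, and how many were tested or seen. Section 5.6.c says the coordinator keeps a tracking sheet that joins ID to patient.

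In Phase 2, the experts review patients with the OMC providers before the initial visit. For those who meet NCCN criteria, the OMC team is to discuss risk assessment and offer testing. Providers remain free to follow the coaching or not.

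Section 10.10 defines an individual research result as "any information collected, generated or discovered in the course of a research study that is linked to the identity of a research participant". Question 10.10.a asks: "Is it anticipated that the research will produce any individual research results that are clinically actionable". It is answered No, and a.1 to a.3 are blank. Section 10.10.d says "Results will be communicated to the OMC provider subjects at the end of phase 1 and phase 2", and that the team and the providers will "discuss the number of patients seen who were eligible for genetic testing, number of those patients who were referred", followed by the numbers with a completed appointment and with testing.

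**The concern.** The Phase 1 review creates information about individual patients that the protocol puts to clinical use in Phase 2. For Phase 1 it states only aggregate feedback. A provider would learn how many of the Phase 1 patients were eligible and how many of those were referred, but not which ones were missed.

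The treating provider is the only available channel. Section 4.2.a rules out contact between the study team and patients, and section 8.2.a provides neither patient consent nor information to patients afterwards. At stake is a missed opportunity: a judgement already made, on a matter the study regards as under-recognised at this site, goes unused for the patients it concerns. The validity of the phase comparison is not in question.

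**Working it through.** No sample size or test figure bears on this point. The check sets the sections side by side and then bounds the size.

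**Does an individual judgement exist?** Yes. A count of patients meeting criteria can only come from classifying each record (5.1). The tracking sheet (5.6.c) makes each classification traceable to a patient, so it falls under the form's broad definition of an individual result.

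**Does the protocol attach an action to it?** In Phase 2, yes: an offer of testing (5.1). Section 2.2.a gives identifying patients to be offered counseling and testing as the purpose of releasing records, without limiting this to Phase 2. Section 3.1 refers to "obstacles to their patients in accessing genetic evaluations for the treatment of their cancers and for their family members". Section 10.9 claims benefit through screening and prevention in relatives. The form counts as actionable those actions that "have the potential to change the clinical course of the disease/condition, or lead to an improved health outcome".

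**Is any return step stated for Phase 1?** None was found.
- 5.1 has no such step, and 10.10.d lists numbers only.
- 5.7.a, 8.2.f and 8.3.e mention meetings or conferences with providers, the last of these over the whole study. But 5.1 places case review in Phase 2, and reviewing Phase 1 patients with providers during Phase 1 would contradict a phase without intervention.
- 10.10.c speaks of uniform recommendation processes but names no step.

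**Are the data for a list already held?** Yes. Counting how many eligible patients were referred and tested (10.10.d) requires that status for each eligible patient, and 10.10.c says the coordinator tracks it.

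**Size.** Patients on the lists = N × e × (1 − u), where
- N = 60, the planned Phase 1 maximum in 2.7, reading 60/120 as 60 of 120 over both phases (60 + 60 = 120);
- e = share meeting NCCN criteria, not given;
- u = share of those with a referral or test recorded, not given.

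Each 10 percentage points of e × (1 − u) is 60 × 0.10 = 6 patients. On purely assumed ranges:
- e = 20% and 1 − u = 50%: 60 × 0.20 × 0.50 = 6 patients;
- e = 60% and 1 − u = 90%: 60 × 0.60 × 0.90 = 32.4, about 32 patients.

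**Workload.** Section 2.7 lists 4 + 1 + 1 = 6 providers, so there are at most 6 lists, with an average of at most 60 / 6 = 10 names if all take part.

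**Timing.** Each phase lasts 3 months, and I assume Phase 2 follows directly. A list sent at month 6 reaches the provider 6 − 3 = 3 months after the latest Phase 1 visit and 6 − 0 = 6 months after the earliest. It is slightly longer if the outcome cut-off falls after month 6.

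**The case against.** A reader might infer that the No at 10.10.a is an error and that a.1 to a.3 were left unfinished. The documents do not support that. Eligibility is a published criterion applied to chart data the provider already holds. It leads to the offer of a test, and only the test result leads to treatment or prevention, so No is a defensible reading. The form asks for a.1 to a.3 only after Yes, so the blanks are correct. What can be said is that No sits badly with 2.2.a, 3.1 and 10.9.

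A reader might also infer that Phase 1 patients are denied care. They are not. They keep their existing care, and the same providers, once coached, may apply what they learn to Phase 1 patients still under their care. That is a possibility, however, and not a stated route.

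Three further objections have force.
- A named list sent between the phases is patient-level expert feedback before Phase 2 and could blur the comparison. This stands, and it is why the later date is preferred below.
- The providers' written procedures, data instructions and consent sheet are not shown and could contain a return step. This stands as a caveat, although 10.10.d is where this document asks for it.
- The 60 is a desired maximum, and section 2.7 sets no firm enrolment limit for minimal-risk research. This stands too; 60 is a planning figure.

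Withholding during Phase 1 is legitimate. The form itself lists as a reason "Returning the results has the potential to cause bias". That reason lapses once the outcomes are counted.

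**Conclusion.** The point holds as a gap in the stated procedure. Phase 1 produces a re-linkable judgement that the study uses for care in Phase 2, and neither 5.1 nor 10.10.d says what becomes of it for Phase 1 patients who are eligible but not referred or tested.

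The form's guidance is "Other clinically actionable results should be offered if this can be accomplished without compromising the research". If the judgement is regarded as actionable, a return made after outcome counting has closed meets that condition, because it can alter neither phase's counts.

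The number of patients cannot be derived from the document. The conclusion rests on the unseen provider materials containing no return step, and the scale on reading 60/120 as 60 in this phase. It is a modest, inexpensive improvement for patients and not a flaw in the comparison.

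**What to change.** Add to 10.10.d: after the Phase 2 outcome data cut-off, the research coordinator sends each treating OMC provider, by secure email, a list of that provider's Phase 1 patients judged to meet NCCN criteria with no referral or test recorded. The list is for use at the provider's discretion. It carries a note that absence from it does not mean criteria are not met, because the Phase 1 family history form was optional. Later referrals or tests of these patients are counted in neither phase.

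The sponsor may choose the Phase 1 cut-off instead if it accepts some added provider learning before Phase 2.

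Amend 10.10.a to a.3 to match:
- a.1: the result is the judgement that criteria are met; it is not urgent.
- a.2: it is offered through the treating provider.
- a.3: it is held back until then to protect the no-intervention baseline and the phase comparison. Judgements that criteria are not met are not returned, because incomplete family history leaves their validity uncertain.

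Since 10.10.f ties return plans to the consent document, the provider information sheet should say the same.

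The cost is a wording change for the IRB and a small coordinator task using data already tracked. Sending identified patients to providers is not new, since the conference agendas in 10.6 already do so. The later date costs the delay shown above; the earlier date shortens it at some risk to the Phase 2 comparison.
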